#### 4.4.4. Data analysis

The data linkages between datasets are complex but our team have prior experience with this (PM, CS, CDO, PG). Data will be processed and linked differently according to approach (patient- versus ward-level, establishment versus deployment decisions). For the patient-level approach, for example, all patient information pertaining to one admission will be linked together, and linked with the acuity/dependency category of the patient (repeated for each time the patient is assessed on the ward). Then these predictions will be aggregated to a ward level. In contrast, for the direct ward-level approach, the variables derived are case-mix variables. This will involve identifying which patients are staying on the ward and linking information about those patients together. To calculate the Safer Nursing Care Tool measure, for each assessment we will calculate the ward staffing requirement using the SNCT multipliers and the counts of patients per acuity/dependency category, and translate this into a per patient measure, whole-time-equivalents per patient (for establishment) or care hours per patient (for deployment). We will consider alternative approaches for how to deal with changing patient information, e.g. where a particular care activity is not recorded every day (missing data), whether to assume it is still needed or not.

In **machine learning** terminology, predicting individual acuity/dependency categories is a classification problem, since there are only limited choices, while predicting ward-level staffing requirements is a prediction problem, since the outcome is continuous. Thus different techniques are likely to be appropriate for these two problems. For the individual-level classification problem, we will begin by implementing ordered logistic regression. Additionally, we will explore using decision trees, random forests(46) and support vector machines, which are well-suited for handling categorical data with a limited number of outcomes. For ward-level regression prediction, we will start with simple approaches like linear regression before extending to other approaches if we meet challenges. We will consider GAM models,(47) random forests, support vector regression, gradient boosting, neural networks, etc., based on the suitability of the data.(48)

We will compare the **predictive performance** of these algorithms and use a split-sample (training/test dataset) approach, which avoids problems with overfitting (when a model is excessively complex, capturing noise rather than the underlying pattern in the training data).(49) By testing our model on a separate dataset, we ensure that our model generalises well beyond the training data. In the first instance, we are aiming to replicate the Safer Nursing Care Tool estimates of staffing requirements as closely as possible. Thus, we will assess how close our estimates/predictions are to the SNCT ones using Bland-Altman limits of agreement(50) and statistics such as root mean squared error. We will calculate these statistics for both the training and test datasets allowing us to monitor any discrepancies between training accuracy and real-world applicability. We will work with our nurse

Ethics/ERGO no: 100780; IRAS no: 346148

representatives to understand what "good enough" looks like and determine suitable thresholds. Other measures such as concordance and comparing ward rankings (i.e. highest to lowest estimated staffing requirement) between measures will also be considered. For establishment-setting decisions, we will take 30-day (the sample size recommended in current SNCT guidance) samples from the observed and predicted values and compare them. If identified as a priority in WS1, we will also look into whether tracking how ward acuity/dependency levels change over time using **statistical process control** charts could help identify when establishment reviews are needed.

We will assess if the algorithms fitted for the original hospitals are effective at predicting nurse staffing requirements more generally. For this we will perform **external validation**, assessing how well the algorithms perform on data from other hospital Trusts and from different time periods. Following development of algorithms for our partner Trusts, we will assess whether the same or similar variables can be derived from at least three other hospital Trusts' systems. We will learn to what extent it is necessary to adapt the method of derivations of variables for different Trusts or potentially remove some variables that cannot be calculated. Then we will test the performance of the algorithms on data from these other Trusts and again assess agreement with the SNCT estimates. This will highlight potential problems with the external validity and transferability of the algorithms. Similarly, we will assess the performance of the algorithms on more recent data from the same Trusts. Other measures of validity will be considered in workstream 3.

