#### 4.4.2. Sample sizes

For **developing the algorithms**, we will use retrospectively collected data from our two partner Trusts. Since the new version of the SNCT launched in October 2023, we will extract data from this date onwards or from when the new tool was embedded in the Trusts. We aim to collect at least one year of data. This covers two staffing establishment reviews where acuity/dependency scores are recorded for at least 30 days, so there will be a minimum of 60 (30 x 2) days' data per ward, although in many wards they collect data much more frequently giving about 730 (2 times per day x 365) data points per ward. Scaled up across wards and two Trusts this will give us in the region of 4,800-58,400 ward shift data points for the ward-level approach (assuming 40 wards per Trust), and approximately 120,000-1,460,000 patient shift data points for the patient-level approach (assuming on average 25 patients per ward). For **external validation** of the algorithms, we will use data from at least three further Trusts, and more recent data from our two partner Trusts (data covering at least 1 year).

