#### Sample sizes

To estimate the sample size for the **perceived staffing adequacy outcomes**, we will assume a similar response rate (85%) as for our previous study. We are aiming to run the micro-survey for at least 9 months including a piloting/training phase of 3 months. We will aim for all eligible wards to complete the micro-survey but will work with Trusts as to what is feasible. In Trusts where SNCT data is only collected during establishment reviews, we will aim for the survey to cover 2 establishment reviews. Based on 20 wards per Trust (average number of wards with micro-survey data from previous study(13)), this would give us between about 1200 (30 day sample x 2 reviews x 20 wards) and 4653 (0.85 completion rate x 9 months x 20 wards) ward days of data per Trust for understanding the relationship between understaffing and perceived staffing adequacy. In total across Trusts this would give us between 6,000-23,265 data points. Based on 626,313 admissions in our previous study corresponding to 5 years' of data from 4 Trusts (NIHR 128056 under review), we estimate that across 5 Trusts in a 9-month period we would have in the region of 100,000 patient admissions for modelling the relationship between understaffing and **patient outcomes**.

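### The training/test split cannot avoid overfitting or ensure generalisation as claimed: rows are clustered by patient and ward, no unit of split is stated, and algorithms are compared on the same test data

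*Protocol*

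**What the plan says.** Section 4.4.4 (Data analysis) of the protocol plans to compare the predictive performance of several algorithms and to "use a split-sample (training/test dataset) approach, which avoids problems with overfitting". It continues: "By testing our model on a separate dataset, we ensure that our model generalises well beyond the training data". RMSE and Bland-Altman limits of agreement are to be calculated in both the training and the test data, and thresholds for adequate agreement are to be worked out with nurse representatives. Only a training and a test dataset are named. No third dataset or resampling scheme for choosing among algorithms is described.

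The same section describes the patient-level rows as "repeated for each time the patient is assessed on the ward". Section 4.4.2 (Sample sizes) gives the rows per ward: "so there will be a minimum of 60 (30 x 2) days' data per ward", with many wards recording far more often, "giving about 730 (2 times per day x 365) data points per ward". Summed over both partner Trusts, the protocol expects "in the region of 4,800-58,400 ward shift data points for the ward-level approach (assuming 40 wards per Trust"). Its count for individual patients, which adds an assumption about ward occupancy, is "approximately 120,000-1,460,000 patient shift data points for the patient-level approach (assuming on average 25 patients per ward").

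The candidate methods run from ordered logistic and linear regression to random forests, support vector methods, boosting and neural networks. Sections 4.4.2 and 4.4.4 also plan external validation, after development, in at least three further Trusts and on more recent data from the two partner Trusts.

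**The concern.** The two claims do not follow from the design described. A held-out set does not stop a model from overfitting; it shows whether it has. Nor does it make a model generalise; it estimates how well it does, for the kind of new data that the held-out set resembles.

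Even that weaker service needs independence between the two sets. Several planned predictors are fixed within an admission (age group, route of admission, long-term conditions, admission diagnosis) or nearly fixed within a ward (funded beds, rooms, single rooms; section 4.4.3). If the same admission or ward supplies rows to both sides, a flexible learner can score well by recognising it rather than by learning what drives staffing need. Comparing several learners on the same test data adds some further optimism for whichever comes out best.

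At stake are the internal accuracy figures and the choice of algorithm family that goes on to external validation and to workstream 3, which takes forward the most promising algorithms.

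**Working it through.** **1. The protocol's row counts reproduce.** With 40 wards in each of 2 Trusts (80 wards) and 25 patients per ward (section 4.4.2):
- Ward-shift rows: 30 × 2 × 80 = 4,800 and 2 × 365 × 80 = 58,400.
- Patient-shift rows: 4,800 × 25 = 120,000 and 58,400 × 25 = 1,460,000.

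**2. Rows per admission (derived, not stated).** The workstream 3 sample-size section gives the admissions: "Based on 626,313 admissions in our previous study corresponding to 5 years' of data from 4 Trusts".
- 626,313 / (5 × 4) = 31,316 per Trust-year, or 62,631 a year for two Trusts.
- Twice daily for a year: 1,460,000 / 62,631 = 23.3.
- Once daily for 60 days: 120,000 / (62,631 × 60/365) = 11.7.
- With that section's rounded 100,000 admissions in 5 Trusts over 9 months (53,333 a year for two Trusts), the range is 13.7 to 27.4.
- If stays are cut off by the two 30-day windows, distinct admissions number 2 × (62,631 × 30/365 + 2,000) = 14,296 and the low end falls to 120,000 / 14,296 = 8.4 (9.4 with the rounded figure).

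These averages combine assumed ward and patient numbers with admissions from an earlier four-Trust study, so they are approximate.

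**3. Overlap if rows were split at random.** Assume a 70/30 split and geometrically distributed rows per admission with mean μ, p = 1/μ. The share of test rows with another row of the same admission in training is 1 − [p / (1 − 0.3(1 − p))]².
- μ = 11.7: 98.6%.
- μ = 23.3: 99.6%.

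**4. Clustering by ward.** The design effect is 1 + (m − 1) × ICC. At an assumed ICC of 0.3:
- m = 60: 18.7, so 4,800 / 18.7 = 257 effective ward-shifts.
- m = 730: 219.7, so 58,400 / 219.7 = 266.

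More rows per ward add almost nothing about new wards.

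**5. Size of the optimism (simulation, all inputs assumed).** The inputs were R² 0.4, four cluster-constant and two varying predictors, a 30% test set and residual ICC 0.1 to 0.8. Ten-nearest-neighbour stood in for a flexible learner; it is not a method the protocol lists. The table gives row-split test RMSE divided by whole-cluster-split test RMSE (1.00 means no optimism).

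| Clusters | Linear regression | Nearest neighbour |
|---|---|---|
| Patients, 12 or 23 rows | 0.98-1.01 | 0.98 down to 0.82 |
| 80 wards, 60 or 365 rows | 0.95-1.00 | 0.90 down to 0.38 |

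**6. Dependence on the predictor mix.** This used 80 wards × 60 days, R² 0.4, nearest neighbour and residual ward ICC 0.1 to 0.5.
- 12 ward-constant and 6 daily predictors: ratio 0.64-0.87.
- 2 constant and 10 varying: 0.90-0.98.
- All varying (predictor ICC 0.1-0.3): 0.94-0.99.

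A separate simulation with the 12 + 6 mix and its own assumed ward effects gave RMSE 0.094 (nearest neighbour) against 0.120 (linear) on a row split, but 0.159 against 0.140 on unseen wards, so the preferred method changed. There the linear ratio was 0.120 / 0.140 = 0.86, outside the range in step 5. With the other two predictor mixes the row split still preferred linear regression.

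**The case against.** The strongest reply is that the fault is imputed. The protocol nowhere says that rows will be split at random, and the unit of split is a detail that an analysis plan, not shown here, may fix. That stands as far as it goes: the missing unit alone would not be a finding. What remains is what the protocol does state, namely two guarantees that a training/test split cannot give, attached to data it describes as repeated and clustered.

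Second, external validation in at least three other Trusts uses unseen wards and patients, so it carries none of this leakage, and a poor choice would show there as worse agreement. This also stands, and it limits the harm to internal error and model choice. It does not remove it. That validation follows development, so it can expose a poor choice but does not make the choice. The later partner-Trust data come from the same wards, so they test time rather than new wards.

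Third, the magnitudes rest on assumptions. Section 4.4.4 starts ward-level work with linear regression, and many ward-level predictors are case-mix summaries that change with the patients. A reader might infer that test error will be far too optimistic and that the wrong algorithm will be picked. The documents do not support this: they give neither an ICC for these models nor the number of ward-constant predictors, and the reversal in step 6 disappeared when most predictors varied within wards. A reader might also put the overlap in step 3 above 99.99%, but that requires every admission to have the mean number of rows.

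Fourth, ward hold-out is the wrong test for later use in the same wards, and patients transfer between wards, so folds cannot keep both wards and patients whole without losing rows. Both points are right, and the fix below allows for them.

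**Conclusion.** The point holds in a conditional form. The claims of avoiding overfitting and ensuring generalisation are wrong as stated, and the split as described does not secure the independence that even an honest assessment needs. If admissions or wards straddle the split, internal RMSE and limits of agreement can be too favourable. Under the assumptions in step 5, the understatement is about 0-5% for linear regression, and for a flexible learner 2-18% with patient clusters and 10-62% with ward clusters. It shrinks to roughly 1-10% for the flexible learner at ICC 0.1 to 0.5 when predictors mostly vary within wards. It is larger, for linear models too, when many predictors are ward-constant. These figures are illustrations, not predictions for this study.

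The change should be made because optimism tends to grow with model flexibility, so it can bear on the ranking of algorithms as well as on reported accuracy. The other-Trust results remain a sound check.

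**What to change.** - In section 4.4.4, replace the verbs *avoids* and *ensure* with wording that the split allows overfitting and generalisation to be assessed.
- Replace the split of unstated unit with grouped cross-validation in the partner-Trust data. Hold out whole patients for the patient-level model. Hold out whole wards for the ward-level model and for aggregated ward predictions, dropping from training the rows of patients who also appear in the held-out wards.
- For intended use in the same wards, add a time-block split with admissions kept whole.
- Tune and select algorithms only within these folds, then report the selected algorithm once on the later-period and new-Trust data.
- Where the two partner Trusts share variables and data access allows, also develop in one and test in the other. Section 8 confines patient-level development and external validation to secure data environments, so this may not always be possible.

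The cost is more computing, some rows lost for transferred patients, and reported accuracy that will probably be less favourable. No new data collection is needed.

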## 4.5. Workstream 3: Validating measures of nurse staffing requirements against patient outcomes and nurse perceptions of inadequate staffing

We will conduct a retrospective observational study to investigate the associations between actual under/over-staffing relative to each candidate measure of staffing requirements and a range of outcomes. One would expect that as staffing increases relative to a measure, the risk of poor patient outcomes and perceptions that staffing is inadequate decreases.(13, 26) In the absence of a gold standard, we will compare model fit against models with staffing requirements measured by the SNCT, as well as against the current ward establishments where possible. For this we will use routine data extracted from hospital IT systems along with an empirical (prospective) micro-survey of nurses (three tick-boxes) to understand perceptions of staffing adequacy.

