**WS3 Objective:** assess the validity of algorithms. **Method:** We will fit regression models to investigate the associations between actual under/over-staffing relative to each candidate measure of staffing requirements and multiple outcomes. For this, we will use routine data extracted from hospital IT systems and a micro-survey of nurses to understand perceptions of staffing adequacy. We will test whether as staffing increases relative to a measure of staffing requirements, the risk of poor patient outcomes and perceptions that staffing is inadequate decreases. We will compare model fit against models with staffing requirements measured by the SNCT.

Timelines: 2.5 years

Ethics/ERGO no: 100780; IRAS no: 346148

**Anticipated impact**: A better match between staffing and workload on hospital wards, more efficient deployment of scarce resources and less time-consuming staffing assessments

**Dissemination:** Open-access journal articles, magazine articles for nurses and videos/posters for the public. We will share results with intended users through workshops and user groups.

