#### 3. Aims and objectives

This study aims to develop a method to measure demand for nursing staff on hospital wards using routine data, to facilitate establishment planning, to monitor staffing adequacy/safety in real-time and to inform safe and efficient deployment of staff. To achieve this we have a number of objectives:

- 1) understand what works and does not work for nurses and nurse managers when using staffing tools, and incorporating this into the design of an algorithm for estimating staffing requirements
- 2) develop statistical/machine learning algorithms to estimate nurse staffing requirements from routinely available patient data, starting with replicating Safer Nursing Care Tool assessments
- 3) assess the validity of algorithms by determining whether staffing below the estimated staffing requirements is associated with adverse patient outcomes/ nurse perceptions of inadequate staffing.

Throughout the study we will engage with patients and the public to understand their experiences of hospital nurse staffing and implications for our algorithm development.

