#### 4.5.2. Variables

We will consider a range of **patient outcome variables**. Our primary patient outcome is mortality within 30 days of admission, as it has a strong association with staffing levels.(5, 17) Other patient outcomes we will model include length of stay, readmissions within 30 days (which both have high strength of evidence for an association with staffing levels according to a recent review)(4) and healthcare-associated conditions such as pneumonia and pressure ulcers (which have moderate evidence).(4) We will limit the latter analyses to surgical patients since for medical patients it is harder to distinguish between complications and conditions present on admission.

Our other outcomes are measures of **perceived staffing adequacy** assessed through the prospective micro-survey. We will ask clinical nurses three questions as in our previous study: i) Were there enough staff for quality?, ii) Were breaks missed? and iii)Was care left undone?(13) These were derived following pilot work of a more extensive set of questions, and are aimed to be quick to answer and give a good indication of overall staffing adequacy on a ward. In our previous study these were all associated with deviation from SNCT-recommended staffing.(13)

Ethics/ERGO no: 100780; IRAS no: 346148

Our **independent variables** are the deviation of actual staffing from measures of staffing required. In other words, under-/over-staffing compared to different measures of what is needed. Actual (achieved) staffing is measured as total care hours per patient day and includes all nursing staff on the ward: both Registered Nurses and Support Workers, both permanent and temporary (bank or agency) staff. Required staffing will be measured in different ways including: using the SNCT, current ward establishments, algorithmic measures (including the ward-level and patient-level approaches).

To start with we will model overall staffing but where possible will also consider **skill mix** by splitting out staff groups. We will use current ward establishments to calculate the planned skill mix and apply these to our alternative measures of staffing requirements. This will allow us, for example, to assess Registered Nurse understaffing and Support Worker understaffing separately, which is important since differing relationships have been found with patient outcomes.(5) We will use the pay band to categorise staff, given the differences in roles and job titles between Trusts.

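### The directional validity test in Workstream 3 can be passed on actual staffing alone, and no raw care-hours reference model is planned

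*Protocol*

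**What the plan says.** Objective 3 (section 3) is to "assess the validity of algorithms by determining whether staffing below the estimated staffing requirements is associated with adverse patient outcomes/ nurse perceptions of inadequate staffing". The Summary of research and section 4.5 express the same idea as a direction: "One would expect that as staffing increases relative to a measure, the risk of poor patient outcomes and perceptions that staffing is inadequate decreases".

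Section 4.5.2 defines the exposure: "Our independent variables are the deviation of actual staffing from measures of staffing required". It lists three sources for the requirement: the SNCT, the ward's current establishment, and the algorithms at ward and patient level.

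Section 4.5 adds a comparison: "we will compare model fit against models with staffing requirements measured by the SNCT, as well as against the current ward establishments where possible". Section 4.5.3 names AIC as the fit criterion and adds decision curves. It sets no AIC margin. Nowhere is there a model with actual care hours alone or with one constant requirement.

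**The concern.** Actual staffing sits inside every exposure, and section 4.5.2 itself chooses 30-day mortality because of its strong link with staffing levels. If fewer hours per patient means worse outcomes, then actual minus almost anything will tend to show the expected sign.

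The realistic case is a near-constant prediction. Workstream 2 fits SNCT values to routine variables, and a regression whose predictors carry little information returns values close to the mean. Section 10 names unsuitable routine data as a risk. The directional test does not detect that failure.

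At stake is the meaning of a positive result. It could be reported as validity of the algorithm when it shows only that fewer hours are worse. Section 5 makes correspondence with outcomes one of the conditions for taking an algorithm on towards software.

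**Working it through.** **The plan's own figures.** Per Trust: 30 × 2 × 20 = 1,200 ward-days, and 0.85 × (365 × 9/12) × 20 = 4,653.75, given as 4653. Over five Trusts: 6,000 and 23,265. Both reproduce.

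**Algebra.** Write A for actual hours, N for true need and R for the measure, and let the log-odds of perceived inadequacy change by −β per hour of (A − N).

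- If R is a constant, A − R is A shifted, so the slope is the slope on A. That is approximately −β × [var(A) − cov(A, N)] / var(A). The sign is as expected whenever var(A) > cov(A, N).
- If R is noise unrelated to A and N, that slope shrinks by var(A) / [var(A) + var(R)] and keeps its sign.

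**Assumed inputs (none is in the protocol).** 100 wards, 6,000 ward-days, β = 0.35 per hour, two-sided 0.05. Ward-mean need has SD 0.5 and daily need within a ward SD 1. The establishment is ward-mean need plus error of SD 0.3. Actual hours are the establishment plus a daily deviation of SD 1 that has correlation ρ with daily need. The SNCT is true need plus error of SD 0.7. There were 60 runs per setting.

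Then var(A) = 0.25 + 0.09 + 1 = 1.34 and cov(A, N) = 0.25 + ρ.

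| ρ | Predicted OR per hour, constant: exp(−0.35 × (1.09 − ρ)/1.34) | Simulated OR | Constant passes | Noise passes |
|---|---|---|---|---|
| 0 | 0.752 | 0.759 | 100% | 100% |
| 0.3 | 0.814 | 0.817 | 100% | 100% |
| 0.6 | 0.880 | 0.881 | 98% | 97% |
| 0.9 | 0.952 | 0.952 | 48% | 28% |
| 1.0 | 0.977 | 0.979 | 18% | 13% |

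Passing means the expected sign with p < 0.05. For noise at ρ = 0.3 the formula gives 0.817^(1.34/2.34) = 0.891, and the simulation gave 0.891. With 60 runs, the 48% has a Monte Carlo standard error of √(0.48 × 0.52/60), about 6 points.

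**Range.** At 23,200 ward-days the constant passed in 100% of runs up to ρ = 0.6, 95% at 0.9 and 43% at 1.0. At 6,000 ward-days and ρ = 0.3 (100 runs), constant and noise passed in 100% and 97% at β = 0.2, and in 70% and 44% at β = 0.1.

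**Does AIC against the SNCT catch it?** (6,000 ward-days, β = 0.35; the two values are for ρ = 0.3 and 0.6)

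| SNCT error SD | AIC of constant minus AIC of SNCT | Runs in which the constant fits better |
|---|---|---|
| 0.7 | +86.7, +52.2 | 0%, 0% |
| 1.5 | +13.8, +7.5 | 25%, 33% |
| 2.5 | −27.4, −11.5 | 95%, 88% |

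At error SD 2.5 pure noise also fitted better than the SNCT in 55% of runs. The fixed establishment behaved much like the constant: 82.9 AIC points behind the SNCT, against 86.7, at ρ = 0.3 and error SD 0.7.

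**Limits.** The models were plain logistic without ward effects or clustered errors, the establishment was taken as a fixed number of hours per patient day, and only perceived adequacy was simulated.

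**The case against.** The strongest reply is that direction is not the whole test. Fit is compared with the SNCT by AIC, decision curves are compared, and multi-level models look at ward-specific fit. Only selected algorithms reach Workstream 3, after agreement with the SNCT has been checked by Bland-Altman limits and RMSE against thresholds agreed with nurses. The establishment does not respond to daily acuity, so it already serves as a partial null comparator, and section 4.5.1 allows it to be estimated from rosters when it cannot be sourced.

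Much of this stands. A reader might infer that the test cannot fail for a useless algorithm, or that no acuity-blind comparator exists. The documents support neither. Against a precise SNCT the AIC comparison rejected the constant in every run at correlations of 0.3 and 0.6, and a random requirement would agree poorly with the SNCT in Workstream 2.

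The guards still leave a gap:

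- AIC against the SNCT has no zero point. It ranks two measures without showing what either adds to actual hours. The protocol cannot take a precise SNCT for granted: it says there is no gold standard and that reliable ratings need considerable training.
- The agreement thresholds are not yet set. The extensions in section 4.4.3 go beyond acuity and dependency on purpose, so agreement with the SNCT is a poor yardstick for them.
- The establishment comparison is conditional, and nothing requires a measure to beat it. Establishments also carry average ward need: in the survey cited in section 2.3, 80% of responding Trusts used the SNCT, with professional judgement, in establishment reviews.

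**Conclusion.** The point holds for the directional criterion, which is how objective 3 defines validity. That criterion does not reliably separate an informative measure from a near-constant one. Under the assumed inputs the constant passes almost always when staffing follows need loosely or moderately, about half the time at correlation 0.9, and seldom at 1.0. It also passes less often when the staffing effect is weak. The true correlation, effect size and SNCT error are unknown, so the percentages illustrate the problem and do not predict results.

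The algebra applies in form to any model with a linear term for the deviation, including survival models. No figure has been derived for mortality, and none should be inferred.

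This is a cheap improvement of moderate severity. It does not invalidate the design, because the planned fit comparison gives partial protection. It concerns how objective 3 is framed, which goes beyond detail that an analysis plan would supply.

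**What to change.** 1. In sections 4.5 and 4.5.3, add for every outcome a reference model whose only staffing term is actual care hours per patient day. This equals one single constant requirement for all wards. Do not use a ward-type mean: SNCT multipliers differ by ward type, so that mean carries information on need.
2. Fit it to the same records with the same covariates and random effects as the models it is compared with. With one staffing coefficient in each model, the AIC difference is then twice the difference in log-likelihood. If staffing is also coded as below or above the requirement, fix one overall constant in advance.
3. Report the AIC gain over this reference for every measure, including the SNCT and the establishment.
4. Reword objective 3 and section 4.5 so that a measure is supported only if the association has the expected direction and its deviation fits better than the raw-hours reference.

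The cost is one extra model per outcome on data already linked, and a change of wording. The downside is that some measures, possibly the SNCT itself, may look less favourable.
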